- 7) analgesic effects due to elevated endorphin production, electrolytic nerve blockage, and improved blood and lymph flow
- 8) anti-inflammatory effect due to improved circulation and accelerated tissue regeneration; and 9) increased production of antioxidants.

Of additional benefit is that light energy from low level lasers will only be absorbed by those cells and tissues that are not functioning normally and that need it. Soft laser light has no effect on healthy cells.

The progressive process by which low level laser light aids in the production of ATP, consequently providing cells with more energy which in turn optimizes the cells' condition to play their part in a natural healing and pain reduction process, is as follows:

The effects of low-level laser light are photo-chemical (not thermal),
triggering normal cellular function.

THEORY OF MECHANISM OF OPERATION OF THE APPLICATION OF LOW-LEVEL LASER THERAPY TO REDUCING CHRONIC DIABETIC PERIPHERAL NEUROPATHY PAIN

Considering the general mechanism of operation of LLLT as explained above, it follows that LLLT provides relief from the foot pain from chronic diabetic peripheral neuropathy by:

- penetrating the skin of the foot and the ligaments and tendons to increase the production of ATP and activate enzymes in the targeted cells of the tissue to promote healing of the tendons and ligaments
- cultivating a growth factor response within the cells and tissue of the foot as a result of the increased ATP production to promote new, healthier cell and tissue growth to strengthen and support ligaments and tendons, to restore mechanical and sensory function, and to protect against further damage
- The anti-inflammatory properties of low-level lasers reduce nerve irritation and inflammation in the foot to provide pain relief

ERCHONIA CORPORATION LLLT LASER DEVICES AND PAIN REDUCTION INDICATIONS

Erchonia Corporation's 635nm red diode and 405nm violet diode low-level lasers have been shown through controlled clinical trials to be effective for pain reduction, as evidenced through the following FDA 510(k) approvals for various pain reduction indications based on the supportive outcome of those clinical trials.

1. **K191257:** *Erchonia® EVRL*: is indicated while using the red and violet diode simultaneously, for adjunctive use in providing temporary relief of minor chronic neck and shoulder pain of musculoskeletal origin.
2. **K180197:** *Erchonia® FX-635*: is indicated for the following two indications:

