3. **K072206: Erchonia® EML Laser:** is indicated for the temporary reduction in post-surgery pain at 24 hours after surgery following bilateral breast augmentation surgery.
4. **K041139: Erchonia® EML Laser:** is indicated as an adjunct to liposuction procedures of the thighs, hips and stomach for reduction of pain associated with the recovery process.
5. **K012580: Erchonia PL2000:** is indicated for adjunctive use in providing temporary relief of minor chronic neck and shoulder pain of musculoskeletal origin.
6. **K191257: Erchonia® EVRL:** is indicated while using the red and violet diode simultaneously, for adjunctive use in providing temporary relief of minor chronic neck and shoulder pain of musculoskeletal origin.

In addition, a previous Erchonia laser emitting 635-640nm line generated laser, received FDA Over The Counter (OTC) indications based on data from a lay person (non-doctor) usability and efficacy trial under 510(k) # **K162578 and K143007**.

DEVICE DESCRIPTION

Performance Characteristics

The Erchonia® EVRL OTC™ Laser will be self-administered by the subject at home. Each EVRL OTC™ administration will last 5 minutes per foot, for a total treatment time of 10 minutes.

The Erchonia EVRL OTC™ Laser is a hand-held single diode, variable hertz laser that is portable, self-contained, lightweight, and battery operated.

The Erchonia® EVRL OTC™ (Model# EVRL) is a low-level laser system that uses two semi-conductor diodes; visible red light: 630-650 nm ($7.5\text{mW} \pm 1\text{mW}$) and visible violet light: 380-450 nm ($<5\text{mW}$). The Erchonia® EVRL OTC™ (Model# EVRL) is a variable hertz device. The variable hertz feature of the Erchonia® EVRL OTC™ (Model# EVRL) is a pulsed wave, defined as containing a selected series of breaks, variances.

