Physical Characteristics

Weight: Laser - .95lbs / .42kgs. Charger Base - .55lbs / .25kgs

(Height x Depth x Width)

Size: **(Laser)** 6.9" x 3.10" x .76"/ 17.52cm x 7.87cm x 1.93cm

Size: **(Charging Base)** 5.7" x 3.5" x 1.65"/ 14.47cm x 8.88cm x 4.19cm

Device

- Full color touch screen control center
- Exterior Materials: 60601-TG AL
- Finishing: Powder Coating and Anodizing Finish

Laser

- Qty: 2, Class 2 line generating diode modules
- Output: (Red) .5mW ±1.00mW
- Output: (Violet) 405 nm <5mW
- Wavelength: Red 640 nm± 10nm
- Wavelength: Violet 405nm± 10nm
- Modulation: Constant Wave- 50% Duty Cycle

Power

- Source: 100-240Vac, 50-60Hz, 0.5A; 12Vdc 1.5A

Temperature

- Operating Temp: 59 to 85°F (15 to 29°C), Relative Humidity: <50%
- Transporting: 14 to 140°F (-10 to 60°C) Relative Humidity: <95%

POWER BUTTON (ON/OFF) [1]

The Power Button allows you to turn the device ON “I” or OFF “O”. To turn the device ON, press and Hold this button, (approximately 4 seconds) until the green (#3 Power On Light) turns on. To turn off the device it is recommended to use the “**Power Down**” icon method, explained in the **Operation** section of this manual. In the unlikely event that your device stops responding to touches, by pressing and holding the power button for 15 seconds will force shut down the device. This is only recommended if the device cannot be turned off from the “**Power Down**” screen method.

LASERS ON LIGHT [2]

The “Lasers On” light is an LED indicator that will light up when the Lasers are ON and shut off when the lasers are OFF

POWER ON LIGHT [3]

The “Power On” light is an LED indicator that will display a constant green light when the device is powered on and shut off only when the device is OFF.

TOUCH SCREEN [4]

The touch screen functions as a display screen and an input panel, providing information and a means to operate the device by touching the appropriate icon.

PIVOTING LASER MOUNT [5]

The Pivoting Laser Mount allows you to adjust the laser angle (up to 20° each direction) based on your preference.

LASER DIODES [6]

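### Do the two different red outputs printed for the study laser (7.5 mW and .5 mW) leave the treatment undefined?

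*Protocol*

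**What the plan says.** Two parts of the protocol's Device Description specify the laser.

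- **Red output.** Performance Characteristics gives 7.5 mW, tolerance 1 mW. Physical Characteristics (Laser) gives "Output: (Red) .5mW ±1.00mW".
- **Violet output.** Below 5 mW in both; the list reads "Output: (Violet) 405 nm <5mW".
- **Modulation.** Performance Characteristics says the variable hertz feature "is a pulsed wave, defined as containing a selected series of breaks, variances". The list says "Modulation: Constant Wave- 50% Duty Cycle".
- **Number of diodes.** Performance Characteristics first says the device "is a hand-held single diode, variable hertz laser", and in the next paragraph describes two diodes, one red and one violet. The component description, the specification list and the Laser Diodes entry all say two.

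The remaining treatment parameters are stated consistently: 5 minutes per foot, 10 minutes per session, twice daily for 3 weeks, 42 sessions. The Device Description also says that the user can only switch the diodes on or off and that the treatment programme is set at the factory. The Statistical Analysis section states that there is no statistical analysis, no primary or secondary outcome measure and no success criterion.

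**The concern.** The laser is the only intervention in this single-group pilot, and the results may be used to design a controlled study. Someone working from the protocol alone would find two red powers that cannot both be true, a wave described as both pulsed and constant, and a stray reference to one diode. If the red figure were really open, the red energy delivered per session would be uncertain by a factor of 15, or 30 if the duty cycle were also in doubt. A pilot result could then not be tied to a known exposure, and an ethics board would see two emitted powers for a laser used at home.

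**Working it through.** The protocol states no energy per session, so there is no figure of its own to reproduce. The check compares the stated versions.

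**Inputs.** Red power 7.5 ± 1 mW (Performance Characteristics) or 0.5 ± 1 mW (Physical Characteristics); violet below 5 mW (both); 300 s per foot and 600 s per session; 42 sessions (Procedure Administration Protocol); duty cycle 50% (Physical Characteristics).

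**Formula.** Energy in joules = power in mW × duty factor × seconds / 1000.

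**1. Red diode alone, duty factor 1.**
- Per foot: 7.5 × 300 / 1000 = 2.25 J against 0.5 × 300 / 1000 = 0.15 J.
- Per session: 7.5 × 600 / 1000 = 4.5 J against 0.5 × 600 / 1000 = 0.30 J.
- Over 42 sessions: 189 J against 12.6 J.
- Ratio of nominal values: 7.5 / 0.5 = 15. At the nearest tolerance limits: 6.5 / 1.5 = 4.3.

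**2. Duty cycle.** A 50% duty cycle applied to both readings halves both energies and leaves the ratio at 15. A ratio of 30 arises only from setting 7.5 mW at full duty against 0.5 mW at half duty: 7.5 / 0.25 = 30. The protocol does not say whether either power is peak or average, so that pairing is an assumption.

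**3. Both diodes, equal duty.** With violet power v, assumed between 0 and 5 mW because only the upper limit is given, the ratio of total energy is (7.5 + v) / (0.5 + v).

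| v (mW) | Ratio |
|---|---|
| 0 | 15.0 |
| 1 | 5.7 |
| 2.5 | 3.3 |
| 5 | 2.3 |

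For total energy at nominal red power and equal duty, 15 is thus the upper end of the range.

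**4. The .5 mW entry itself.** 0.5 - 1.0 = -0.5 mW, which is physically impossible, and the tolerance is twice the nominal value. The tolerance is the same 1 mW as in the other section. This is what an entry with a lost character would look like, whether the loss occurred in typing or in conversion of the document. It does not establish which figure is right.

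**5. The other items.**
- Wavelengths agree: red 630-650 nm is the same as 640 ± 10 nm, and violet 405 ± 10 nm (395-415 nm) lies inside 380-450 nm.
- A 50% duty cycle means the beam is off half the time, which fits a pulsed wave. Only the words for constant wave clash.
- The one-diode phrase stands alone against several statements of two.

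**The case for a change.** The strongest case for a change is that this is the specification of the treatment itself. A lost digit is plausible but not proven: the same list writes other values below one without a leading zero (.95 lbs, .42 kgs), so .5 mW can be read as 0.5 mW in the document's own style. A lost digit would not explain the modulation wording either. The protocol's supporting literature also treats exposure as important. In the rabbit nerve study it summarises, 4 W inhibited regeneration while 2 W improved it, so even a two-fold difference may matter on the sponsor's own reasoning. The correction would cost a few lines of text.

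Part of this stands. The red entries conflict, the modulation label is unclear, and both must be reconciled by the sponsor against the device specification. The rabbit study used a different laser at powers in watts, so it sets no scale for this device. More importantly, the objection concerns what is written about the device. It does not show that the device delivered different amounts to different people. All subjects follow the same treatment protocol with preset units, and the pilot's observations belong to those units whatever the list says. A later study could take the output from the manufacturer's record.

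**Conclusion.** The inconsistency is real but clerical, and no change to the design, conduct or analysis follows from it. The red nominal powers differ 15-fold on paper (4.3-fold at the nearest tolerance limits). Total two-diode energy at equal duty differs by about 2.3- to 15-fold, depending on a violet output given only as an upper limit. The device's actual output does not depend on which figure is printed: it is preset, the user cannot alter it, and session length and number are fixed. With no planned statistical analysis, outcome measure or success criterion, no sample size, test or conclusion rests on the printed power.

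This assumes that the shipped units share one factory setting, as the Device Description and Device Shipment sections imply, and that the sponsor holds a record of it. Which figure is correct is for the sponsor to establish. The device entries should be reconciled when the document is next edited.

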neurons. The primary rat cortical neurons were used for further optimization of energy density for 980 nm wavelength light using measurement of total neurite length as the bioassay. For these experiments, the parameters included a 1 W output power, power density of 10 mW/cm², and energy densities of 0.01, 0.1, 0.5, 2, 10, 50, 200, 1,000, and 5,000 mJ/cm². For translation of the in vitro data for use in vivo it was necessary to determine the transcutaneous penetration of 980 nm wavelength light to the level of the peroneal nerve. Two anesthetized, male White New Zealand rabbits were used for these experiments. The output power of the laser was set at 1.0 or 4.0 W. Power density measurements were taken at the surface of the skin, sub-dermally, and at the level of the nerve. Laser parameters used in the in vivo studies were calculated based on data from the in vitro studies and the light penetration measurements. For the in vivo experiments, a total of 22 White New Zealand rabbits (2.34-2.89 kg) were used. Translated dosing parameters were refined in a pilot study using a transection model of the peroneal nerve in rabbits. Output powers of 2 and 4 W were tested. For the final set of in vivo experiments, the same transection nerve injury model was used. An energy density of 10 mW/cm² at the level of the peroneal nerve was selected and the laser parameters were further refined. The dosing parameters used were: 1.5 W output power, 43 seconds exposure, 8 cm² area and a total energy of 65 J.

RESULTS: In vitro, 980 nm wavelength light at 10 mW/cm² significantly improved neurite elongation at energy densities between 2 and 200 mJ/cm². In vivo penetration of the infrared light measured in anesthetized rabbits showed that on average, 2.45% of the light applied to the skin reached the depth of the peroneal nerve. The in vivo pilot study data revealed that the 4 W parameters inhibited nerve regeneration while the 2 W parameters significantly improved axonal regrowth. For the final set of experiments, the irradiated group performed significantly better in the toe spread reflex test compared to the control group from week 7 post-injury, and the average length of motor endplates returned to uninjured levels.

The chronic pain of diabetic peripheral neuropathy can be debilitating, impacting the individual's day-to-day functionality that further leads to physical, cognitive, psychological, sleep and social impairments. Additionally, diabetic neuropathic pain patients are typically burdensome to the health care system, frequently seeking relief from the persistent pain. Many afflicted also suffer economically, as coping with the chronic pain of the condition may render them unemployable or under-employed.

Current therapeutic approaches for managing the chronic pain of diabetic peripheral neuropathy are primarily over-the-counter and prescription medications. However, in addition to their general limited effectiveness, many have harmful side effects with prolonged use such as stomach irritation and bleeding, kidney and liver damage, prevention of wound healing, elevated blood pressure and heart rate problems which can be both more likely to occur and more likely to pose serious implications for individuals with diabetes. Additional potential side effects include dizziness, drowsiness, weight gain, dry mouth, and dry eyes, as well as the potential for addiction with certain prescription medications. Non-medication alternatives are also of limited effectiveness and most, including injections of local anesthetics, surgical destruction of nerves, device implantation and transcutaneous electrotherapy and percutaneous electrical nerve stimulation are costly, invasive and carry their own set of potentially harmful and lasting side effects.

Low level laser light therapy, such as that provided through application of the Erchonia® EVRL OTC™ Laser as proposed in this study protocol, offers a simple, quick, non-invasive, safe, effective and side-effect free option to reduce diabetic peripheral neuropathy pain. Prior trials with Erchonia low level lasers have demonstrated their efficacy in reducing chronic pain in various clinically diagnosed chronic pain conditions, and in post-surgical pain, in a clinically meaningful and statistically significant manner, as is the treatment goal being evaluated in the current clinical study.

Specific Justification for the use of the Erchonia® EVRL OTC™ device for Over-the-Counter application to reduce chronic pain arising from diabetic peripheral neuropathy is found through the following FDA clearances for Erchonia® low level laser devices for chronic pain reduction indications. Each device of which was considered a non-significant risk (NSR), and there were no reported side effects related to the device treatment(s).

1. **K180197: Erchonia® FX-635:** is indicated for the following two indications:
 - a. as an adjunct to provide relief of minor chronic low back pain of musculoskeletal origin.
 - b. as an adjunct to reducing chronic heel pain arising from plantar fasciitis.
2. **K132940: Erchonia® Allay™:** is indicated as an adjunct to reducing chronic heel pain arising from plantar fasciitis.
3. **K072206: Erchonia® EML Laser:** is indicated for the temporary reduction in post-surgery pain at 24 hours after surgery following bilateral breast augmentation surgery.
4. **K041139: Erchonia® EML Laser:** is indicated as an adjunct to liposuction procedures of the thighs, hips and stomach for reduction of pain associated with the recovery process.
5. **K012580: Erchonia PL2000:** is indicated for adjunctive use in providing temporary relief of minor chronic neck and shoulder pain of musculoskeletal origin.
6. **K191257: Erchonia® EVRL:** is indicated while using the red and violet diode simultaneously, for adjunctive use in providing temporary relief of minor chronic neck and shoulder pain of musculoskeletal origin.

LLLT is as safe as it is effective, there are no known side effects of this form of light therapy. The only known potential adverse event associated with the use of laser devices is that long-term exposure to laser light could cause damage to eyesight. As a precaution, during all laser treatment administrations with the Erchonia® EVRL OTC the subject will wear safety glasses that filter out the laser light spectrum. There are no other known potential adverse events from application of the study lasers. There have been no observed or reported adverse events or reactions to the application of the family of Erchonia® laser devices in several other studies using these laser devices.

Previous, Over the Counter (OTC) use of the Erchonia laser has been proven in a lay person (non-doctor) usability and efficacy clinical trial which received FDA OTC clearance under 510(k) # **K162578 and K143007**. In this clinical study the lay person was provided a device operational manual for guidance on the treatment protocol and administration, no training was provided by the study sponsor.

Results showed device operation by the lay persons achieved equal or greater circumference reduction (6.2”) compared to the device administration from a licensed physician (3.54”), in the previous prescription-based FDA study using the identical device. Thus, proving the lay person’s ability to safely and correctly administer the Erchonia laser treatment.

STUDY DESIGN

This pilot study is a non-blinded, single group evaluation of the effect of the Erchonia® EVRL OTC™ on providing relief from chronic pain arising from diabetic peripheral neuropathy.

SUBJECT GROUP

All subjects will be test subjects; that is, all study subjects will receive the active Erchonia® EVRL OTC laser treatment.

NON-BLINDED DESIGN

This pilot study will be non-blinded, such that both subjects and the investigator(s) will be aware that they are receiving the study procedures with active (true) Erchonia® EVRL OTC laser device.

NON-RANDOMIZED

This pilot study is a non-randomized design, wherein all subjects receive the active procedure administrations and the same treatment protocol.

COMPENSATION

A subject will not receive financial compensation for his or her participation in this clinical study.

A subject will not be charged for the cost of the study procedures with the Erchonia® EVRL OTC™ Laser or for the cost of any other directly related evaluations or measurements that occur as part of his or her participation in the study.

SAMPLE SIZE

There will be 10 qualified subjects enrolled in this pilot study.

STUDY PROCEDURE

STUDY TEST BATTERY

The following is a list and description of the study assessment tools to be used and the variables to be recorded in this clinical study. At each evaluation point, the precise tools and variables from this list that will be employed will be specified.

BASELINE VARIABLES

A. Neuropathy Variables

- Number of months/years since onset of foot pain.
- Number of months/years since diabetes diagnosis
- Insulin dependency

B. Medication and Treatment

- *Prior treatment approaches for diabetic peripheral neuropathy foot pain:* Record all prior treatments, whether conventional or alternative, tried by the subject for pain reduction.
- *Concomitant Medication and Therapy Use:* Record all over-the-counter and prescription medications currently used for any indication (other than the management of neuropathy pain symptoms)

C. Subject Demographics: Subject age, gender and ethnicity are recorded.

OUTCOME ASSESSMENT TOOLS

Numerical Rating Scale (NRS)

The Numerical Rating Scale (NRS) will be used to capture the self-reported daily impact of the subject's foot pain. With 1 being "No Pain" and 100 being "Worst possible Pain"

NUMERICAL RATING SCALE: FOOT PAIN

How does the subject rate his or her Foot Pain on a scale of 1 to 100? With 1 being "No Pain" and 100 being "Worst possible Pain".

FOOT PAIN SCORE: _____ /100

Subject Satisfaction with Study Outcome

The subject is asked to rate how satisfied he or she is with any change in his or her overall foot pain following completion of the laser administration procedures with the Erchonia® EVRL OTC™ by using the 5-point Likert scale presented below to respond to the following question: "Overall, how satisfied or dissatisfied are you with any change in your foot pain following the study procedures with the study laser device?"

- Very Satisfied
- Somewhat Satisfied
- Neither Satisfied nor Dissatisfied
- Not Very Satisfied
- Not at All Satisfied

STUDY PROCEDURE PROTOCOL

STUDY QUALIFICATION

SIGNING OF INFORMED CONSENT FORM

The potential participant will be sent an electronic informed consent (eIC) in accordance to “*FDA Guidance for Institutional Review Boards, Investigators, and Sponsors, Use of Electronic Informed Consent, Questions and Answers, December 2016*”. It is the responsibility of the Study Investigator to obtain the eIC. The subject will be provided sufficient opportunity to consider whether to participate (see 45 CFR 46.116 and 21 CFR 50.20). This may be accomplished by discussions with the study investigator through a combination of electronic messaging, telephone calls, video conferencing, or a live chat. When live chat or video conferencing is used during the eIC process, the study investigator will remind subjects to conduct the eIC discussion in a private location to help ensure privacy and confidentiality.

The potential participant must be willing to provide electronic signature in the provided econsent platform that is 21 CFR Part 11 compliant and include a method for verifying identity, such as a birth certificate, government-issued passport, or a driver’s license.

ASSIGNMENT OF SUBJECT IDENTIFICATION NUMBER

The subject is assigned a unique subject identification number based upon his or her order of entry into the study.

Additional information about the informed consent and subject ID number assignment is contained in a later section of the protocol titled, “SAFETY AND CONFIDENTIALITY ISSUES.”

STUDY QUALIFICATION CHECKLIST

In order to be eligible for study participation a subject the following qualifications must be met:

INCLUSION CRITERIA PART 1

To be eligible for study participation, a subject must satisfy each of the following criteria.

- Previously diagnosed with diabetes induced Peripheral Neuropathy by a qualified health Physician.
- Over the age of 18 years of age
- Able to read and write English.
- Constant feet pain on-going over at least the past 3 months.
- Subject is willing and able to refrain from consuming any OTC and/or prescription medications including muscle relaxants and/or herbal supplements and/or recreational and medical drugs including cannabis intended for the relief of pain and/or inflammation throughout the course of study participation, except for the study-specific pain relief medication of OTC Tylenol.

- Subject is willing and able to refrain from engaging in any non-study procedure therapies for the management of foot pain throughout the course of study participation, including conventional therapies such as physical therapy, occupational therapy and hot or cold packs, as well as alternative therapies such as chiropractic care and acupuncture.
- Self-reported foot pain on the Numerical Rating Scale (NRS) is 50 or greater

EXCLUSION CRITERIA

A subject who satisfies any of the following criteria will be excluded from study participation:

- Pregnant or think you might be pregnant.
- Open wounds (sores, cuts, ulcers, etc) around the feet
- Cancerous growths around the feet

PRE-PROCEDURE ACTIVITIES

DEVICE SHIPMENT

The qualified subject will be shipped a Erchonia® EVRL OTC™ device, that is preset and cannot be altered by the end user. Additionally, the subject will be shipped Erchonia® EVRL OTC™ Operation Manual and Treatment Log Form.

PRE-PROCEDURE EVALUATION PHASE

The pre-procedure evaluation phase commences following the delivery of the Erchonia® EVRL OTC™ device to the subject. During pre-procedure evaluation, the following is recorded over videoconference or telemedicine:

BASELINE VARIABLES

- Baseline Foot Variables
- Baseline Concomitant Medication and Therapy Use
- Subject Demographics

PRE-PROCEDURE OUTCOME ASSESSMENTS

- Numerical rating scale: Foot pain

PROCEDURE ADMINISTRATION PROTOCOL

- The procedure administration phase of the study commences following completion of the pre-procedure phase, on the same day or up to 15 days later.
- The procedure administration phase extends over 3 consecutive weeks.

ERCHONIA® EVRL OTC™ DIABETIC PERIPHERAL NEUROPATHY FOOT PAIN PILOT STUDY:
Study Protocol

- Each subject receives 42 total procedures with the Erchonia® EVRL OTC™: twice daily procedure administrations for 3 weeks.
- Each procedure administration lasts 10 minutes.
- Each procedure administration is completed at the subject's home.
- Each subject will be provided a "Operation Manual" that details the laser use and treatment administration.
- Each subject will be provided a "Treatment Log Form" to document each time the treatment is administered.

➤ **Procedure administration protocol is as follows:**

1. The subject seats comfortably in a chair and is correctly fitted with the provided safety goggles.
2. The Erchonia® EVRL OTC™ laser is held at the top of the right foot, at a distance of approximately 3-6 inches from the skin throughout the entire treatment.

Note: The laser lights will cover the top of ankle joint and beyond the toes. (*shown in Fig 2*)

[figure not shown]

Fig 1. Treatment

Fig 2. Treatment Close Up

3. The Erchonia® EVRL OTC™ is then activated for 5 minutes.
4. Step 2-3 is then repeated over the left foot. Both the right and left foot will receive 5-minute treatment each.
5. The subject's protective eyewear is then removed, and the session is over.

PROCEDURE ADMINISTRATION PHASE MEASURES

